5.4 CONCOMITANT MEDICATIONS AND PRECAUTIONS

Concomitant medications will be recorded during the study period from the time of study drug initiation until day-7 or discharge (whichever is earlier). There are few restrictions on the use of concomitant medications for study

participants. The use of prochloroperazine (compazine), a phenothiazine derivative, is not allowed before treatment, during treatment, or up to 72 hours after completion of the study drug infusion, since the combination of DFO and compazine can lead to impairment of consciousness [Blake, 1985]. Concurrent use of other experimental therapy is not allowed. Vitamin C supplements will not be allowed in patients with heart failure during treatment with DFO.

All standard therapies used in the management of ICH patients will be allowed under close monitoring and supervision. These include volume expansion with normal saline or crystalloids, vasopressors, antiedema agents such as steroids or mannitol, anti-hypertensives including diuretics, anti-convulsants, anti-arrhythmic agents and anti-emetics, except for phenothiazine derivatives.

In order to minimize the variability in care and to assure consistency in management across sites, the general care of ICH patients should conform to the guidelines from the Stroke Council of the American Heart Association [Morgenstern, 2010], and the European Stroke Initiative Guidelines [Steiner, 2006]. Pertinent issues are detailed in Appendix II and III.

6 CLINICAL AND LABORATORY EVALUATIONS

6.1 PATIENT EVALUATION AND DATA COLLECTION SCHEDULE

All study data will be collected using Case Report Forms (CRFs) designed specifically for the study. Patient confidentiality will be maintained throughout, as participants will only be identified on the CRFs by a unique study ID number. Patients' identifying information and source documents for the CRF data should be kept by the primary investigator at each participating site. The data obtained will include: 1) Demographics; 2) Previous medical history; 3) Concomitant medications; 4) Vital signs; 5) Results of laboratory tests; 6) NIHSS and GCS scores; 7) ICH score; 8) mRS, SIS-16, and MoCA scores; 9) Adverse events; 10) Surgical and non-surgical treatments; and 11) Imaging findings, including chest x-rays, and CT and MRI scans identifying the location of ICH, presence of IVH or hydrocephalus, and etiology of ICH (after completing diagnostic work-up).

6.1.1 CLINICAL AND LABORATORY ASSESSMENTS

The following assessments will be carried out throughout the 90-day study period:

Upon screening of potential study subjects: 1) Review of head CT and determination of the time of ICH onset or the time the patient was last known to be without presenting deficits; 2) Demographic data; 3) Medical history; 4) Review of medications; 5) General physical examination; 6) Neurological examination, including NIHSS and GCS; 7) Visual and auditory assessment (which includes assessments for cataracts, visual loss or field cut, disturbed color vision, hearing loss, and presence of tinnitus), whenever possible in awake patients; 8) Determination of pre-morbid mRS; 9) Review of admission laboratory tests - Hematology [hemoglobin, hematocrit, red blood cell count and platelet count]; Coagulation [partial thromboplastin time and international normalized ratio]; and serum albumin; and 10) Review of all inclusion/exclusion criteria. A baseline chest x-ray is required to rule out the presence of bilateral pulmonary infiltrates or pulmonary edema. A pregnancy test is required for all women of childbearing potential prior to enrollment into the study. Subjects in whom all eligibility criteria are met should be considered for enrollment, and those who agree to participate via signed and dated informed consent should be enrolled.

Participants should be reassessed immediately prior to the study drug administration to obtain a pre-treatment baseline. **The Pre-treatment baseline reassessments include:** 1) Vital signs, including blood pressure and heart rate; 2)

Neurological examination, including NIHSS and GCS to confirm stability of their neurological status and to obtain pre-treatment baseline scores; and 3) Assessment for new adverse events since screening. Patients who exhibit significant clinical or neurological deterioration (i.e. develop fixed dilated pupils or GCS decreases to ≤ 6) prior to administration of the first dose of the study drug should not receive the study drug, and their participation will be terminated.

Administration of the study drug should only be permitted after obtaining pre-treatment blood sample for serum chemistry and glucose, hepatic function tests, and urine analysis (if not already done upon arrival to the ED).

Subjects who receive the study drug(s) will be evaluated daily for the first 3 days (during study drug infusion while in hospital) and on day-7 or discharge from the hospital, whichever occurs first. Clinic visits will take place on days 30 ± 7 and 90 ± 7 . Telephone interviews will be conducted on day 60 ± 7 and 180 ± 7 .

The following assessments should be performed **after each daily infusion** (every 24 ± 6 h) and through the day following completion of the last infusion: 1) General physical examination; 2) Visual and auditory assessments; 3) Neurological examination, including NIHSS and GCS; and 4) Vital signs, including blood pressure and heart rate. A repeat head CT scan and blood samples for hematology, serum chemistry, renal and hepatic function tests, coagulation studies, and urine analysis should be obtained within 24 ± 6 h following the last infusion of the study drug. Vital signs (blood pressure and pulse) and neurological functions should be assessed at least once every 4h during intravenous drug infusions. Daily urinary output checks should be carried out every day until the day following the last infusion. In addition, the following data must be checked at least once daily for all intubated patients (or more frequently in patients with changes in respiratory status requiring changes in ventilator settings and increased oxygen requirement) throughout day-7 or discharge and entered into Web-DCU™: 1) $\text{PaO}_2/\text{FiO}_2$ ratio; 2) Plateau and peak pressures; and 3) Chest X-ray results (when available). **A chest x-ray is required if the $\text{PaO}_2/\text{FiO}_2$ ratio is < 300 .**

On day-7 or Discharge (whichever comes first), the following assessments are done: mRS, NIHSS, GCS, MoCA and visual and auditory assessments.

During hospitalization, the NIHSS and GCS should be done any time a subject's neurological status deteriorates, or whenever the investigator believes it is prudent to do an assessment. Laboratory assessments beyond those required for the study should be done whenever clinically indicated.

The **Day-30 (± 7)** will be an in-person visit comprised of a general physical examination, visual and auditory assessments, review of SAEs, and assessments of NIHSS, SIS-16, MoCA and mRS.

The **Day-60 (± 7)** assessments, which will be completed via telephone, will be comprised of a functional assessment to obtain a score on mRS and query for SAEs.

The **Day-90 (± 7)** visit will be an in-person visit comprised of a general physical examination, visual and auditory assessments, and assessments of NIHSS, MoCA, SIS-16, and mRS. However, a telephone interview to obtain a score on mRS (the primary outcome measure) may be allowed on a case-by-case basis, after consultation with the PI, if the subject is unable to return for an in-person evaluation.

The **Day-180 (± 7)** assessments, which will be completed via telephone, will be comprised of a functional assessment to obtain a score on mRS.

A study staff member certified in NIHSS and mRS and experienced in administering GCS, SIS-16, and MoCA should perform the assessments at all time points. We require that all assessments at all time points be performed by the same blinded

investigator, whenever possible, to minimize inter-rater variability. Data on the subject’s functional status (mRS and SIS-16) can be obtained from a proxy if the subject is unable to provide the information. Please refer to Appendix V for details of NIHSS, GCS, SIS-16, and MoCA scales.

Concomitant medications and non-drug therapies should be assessed at all points of contact with the subject after study drug initiation. All adverse events (serious and non-serious) should be assessed until day-7 or discharge, whichever occurs first. All new SAEs will be monitored until day-90, resolution of the SAE, or withdrawal of consent, whichever is earlier. Continuing SAEs beyond day-90 will be monitored until day-180.

6.1.2 RADIOLOGICAL ASSESSMENTS

A baseline pre-treatment non-enhanced brain CT confirming the presence of ICH is required to establish the diagnosis of ICH. The need for additional diagnostic tests, such as CTA, MRI/MRA, or a conventional angiogram to rule out secondary causes of ICH in suspected cases should be based on the judgment of the investigators according to the standards of clinical practice at each participating institution and the guidelines from the ASA [Morgenstern 2010; refer to Appendix II]. The volume of ICH on admission scan must be determined by the local investigators using the ABC/2 method (please refer to Appendix IV for instructions) before randomizing the subject in WebDCU™. A repeat non-enhanced brain CT scan should be obtained within 24±6 hours after completion of the last infusion, with the same standard imaging protocols and scanner at a given hospital. Additional CT scans, beyond those required for the study, should be done whenever clinically indicated.

A baseline chest x-ray confirming the absence of bilateral pulmonary infiltrates or pulmonary edema is required before considering the subject for enrollment into the study. A repeat chest x-ray is required in intubated patients whenever the PaO₂/FiO₂ ratio is <300.

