1.3 EXPLORATORY OBJECTIVES

Additional planned exploratory analyses include assessments of:

- The effects of treatment with DFO on relative perihematoma edema (PHE) volume progression between baseline and post-treatment CT scans in DFO-treated patients compared to placebo as potential markers of DFO's biological activity on brain tissue.
- Whether the effect of DFO on outcome is dependent on initial ICH volume, after adjusting for other confounding variables that can affect outcome, to determine if specific limits for ICH volume should be specified as exclusion/inclusion criteria for future studies.

- The effects of DFO on the size of ventricular enlargement in patients with intraventricular extension of ICH, not requiring an external ventricular drain (EVD), as a potential marker of treatment utility in intraventricular hemorrhage (IVH).
- The effect of DFO on the incidence of symptomatic cerebral edema (unexplained increase in NIHSS >4 points or decrease in GCS >2 points) during hospitalization, up to day 7 or discharge, whichever is earlier.
- Whether progression of PHE can be a radiological/biological marker of activity that can be correlated with clinical outcomes and treatment effect of DFO.

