PHYSIOLOGICAL DATA: Laboratory data - There were no differences in routine laboratory values and in the incidence of abnormalities and change from baseline in EKG parameters. Overall, daily DFO infusions at a rate of 7.5 mg/kg/hour up to 62 mg/kg/day (up to a maximum of 6000 mg/day) were well tolerated without significant alterations of hemoglobin or hematocrit, hematological parameters, and renal or hepatic functions. Treatment with DFO for 3 consecutive days at all 5 dose-tiers did not result in iron deficiency. Overall, the median values of the change in iron parameters from baseline to after the 3rd DFO infusion were as follows: serum iron (3.5 ug/dl; 95% CI -23, 45); transferrin (-18 ng/ml; 95% CI -43, 5); total iron binding capacity (8.5 ug/dl; 95% CI -47, 30); and ferritin (32.5 ng/ml; 95% CI 6, 74). We found no relationship between DFO dose and changes in serum iron studies. Vital signs (heart rate, respiratory rate, oxygen saturation, and temperature) - Overall, DFO administration did not result in important alterations in these variables. Blood pressure: DFO had a moderate BP-lowering effect. Overall, the median mean BP at baseline was 95.8 mmHg (95% CI 84, 100.3) vs. 93.2 mmHg (95% CI 87.6, 98) during the infusions. A total of 8 patients (40%) experienced a maximal drop in mean BP >20% (median 0.29; 95%CI 0.27, 0.39) at some point during the infusions compared to baseline values. One subject required vasopressors; his hypotension was thought to be related to intubation and anesthesia. None of the remaining 7 subjects required any medical treatment.

RADIOLOGICAL DATA: We found no radiological evidence to suggest that treatment with DFO exacerbates the natural enlargement of ICH or PHE over 72h after treatment. The overall median change in relative PHE volume from screening to post-3rd DFO infusion was 0.48 (95% CI 0.10, 0.76) and from screening to day-7 or discharge (whichever

occurred first) was 0.87 (95% CI 0.51, 1.28). These exploratory results contrast with previous studies of the natural history of relative PHE evolution [Mehdiratta 2008; Gebel 2002], which showed that the relative PHE volume almost doubles by 72h.

FUNCTIONAL OUTCOME DATA: Two subjects withdrew consent, one after the 7-day visit (mRS =5), and one after the 30-day visit (mRS =1). Among the remaining 18 subjects, 9 subjects (50%) had mRS scores of 0-2; 2 (11%) had a score of 3; and 7 (39%) had scores of 4-6. The 90-day mortality rate was 15%.

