SURROGATE MEASURES OF DFO BIOLOGICAL ACTIVITY: We plan to examine the effect of treatment with DFO on relative PHE volume and progression at days 3-4 as a surrogate marker of biological activity on brain tissue. Delayed brain edema formation following the first 24h after ICH is related to red blood cells' lysis and hemoglobin- and iron-mediated toxicity [Xi 1998/2002; Lee 1996; Qing 2009]. Treatment with DFO reduces brain edema, CSF free iron levels, iron deposition in the perihematoma region, and residual cavity volume after experimental ICH [Nakamura 2003-2004; Wan 2006-2009; Gu 2009; Okauchi 2009]. Human studies suggest that PHE continues to grow for weeks after ICH, and that edema progression is fastest during the first few days [Venkatasubramanian 2011]. Although the influence of PHE on long-term recovery after ICH is debatable [Hua 2002; Inaji 2003; Zazulia 1999; McCarron 1999; Sykora 2009; Sansing 2011], there is evidence that early edema progression correlates with early neurological deterioration [Venkatasubramanian 2011; Inaji 2003]. Therefore, secondary analyses will examine the effects of treatment on PHE immediately following completion of the infusion and not weeks later, since PHE growth during the early time period seems to be more clinically relevant. Regardless of the clinical impact of PHE, demonstrating an effect of DFO on this variable would at least provide secondary evidence of the agent's biological activity under the chosen dosing regimen. The relative PHE volume (the absolute PHE volume divided by the hematoma volume) was chosen as it has been used previously to detect serial changes in edema volume while adjusting for subsequent hematoma expansion or retraction [Gebel 2002; Mehdiratta 2008].

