• Post-treatment scan should be performed within 24±6 hours of the last infusion even if it is terminated before day-5 of treatment
⁹⁶ A telephone interview to obtain a score on mRS (the primary outcome measure) may be allowed on a case-by-case basis if the subject is unable to return for an in-person evaluation on day 90.
⁹⁶ Chest x-ray must be performed in any intubated patient if PaO₂/FiO₂ ratio is <300.

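### The only required follow-up CT is timed from the last infusion given, so subjects stopped early are scanned one to two days before the intended days 3-4

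*Protocol*

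**What the plan says.** Section 6.1.2 sets the follow-up scan: "A repeat non-enhanced brain CT scan should be obtained within 24±6 hours after completion of the last infusion". Section 6.1.1 repeats the rule for the CT and the safety laboratory tests together, which "should be obtained within 24 ± 6 h following the last infusion of the study drug". A footnote to Table 6.2 extends it to early stoppers: "Post-treatment scan should be performed within 24±6 hours of the last infusion even if it is terminated before day-5 of treatment". No other follow-up CT has a fixed time; further scans are left to clinical need.

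Section 1.3 uses this scan for an exploratory objective: "relative perihematoma edema (PHE) volume progression between baseline and post-treatment CT scans in DFO-treated patients compared to placebo". A further objective there correlates PHE progression with clinical outcome. Section 3.3 gives the intended time, planning to examine "relative PHE volume and progression at days 3-4 as a surrogate marker of biological activity on brain tissue", and notes that "edema progression is fastest during the first few days".

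Section 8.3 keeps subjects in the modified intent-to-treat sample once the infusion has begun, even if it is stopped early. Section 7.4 keeps subjects who stop the drug but do not withdraw consent in follow-up to day 180.

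**The concern.** For a subject who completes treatment, a scan about a day after the last infusion and a scan at days 3-4 are the same scan. For a subject who stops early they are not: the clock starts sooner, the scan comes sooner, and it records less of that subject's own edema growth.

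Stopping happens after randomization and may differ by arm. If it does, a difference in scan time enters the PHE comparison and can be read as biological activity of the drug. The correlation of PHE with outcome is exposed even if stopping is equal in the two arms. Subjects stopped for complications plausibly do worse, yet their edema would be read early and therefore low.

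The footnote that governs early stoppers also refers to day 5 of treatment, whereas sections 3.2 and 5.1 describe a 3-day course.

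**Working it through.** **Inputs**
- Dose 32 mg/kg/day for 3 consecutive days, at no more than 7.5 mg/kg/h (section 5.1).
- Scan 24±6 h after the last infusion (sections 6.1.1, 6.1.2 and 6.2).
- Phase I (section 2.2.2): "The overall median change in relative PHE volume from screening to post-3rd DFO infusion was 0.48" (95% CI 0.10 to 0.76), and 0.87 by day 7 or discharge, so PHE was still rising after the third infusion.
- Share stopping early, by arm: not given. Assumed excess in one arm: 5%, 10% or 20%.
- Shape of growth up to the completer scan: not given. Assumed linear, or square-root in time (faster early on).

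**Step 1: scan times from treatment start.** The shortest infusion takes 32/7.5 = 4.27 h. If infusion k is the last, the scan falls at 24(k−1) + 4.27 + 24 ± 6 h.
- k = 3: 76.3 ± 6, about 70-82 h. This agrees with the plan's own target of days 3-4.
- k = 2: 52.3 ± 6, about 46-58 h.
- k = 1: 28.3 ± 6, about 22-34 h.

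The three windows do not overlap. Slower infusions move all three later by the same amount, so the gaps of 24 h and 48 h remain.

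**Step 2: growth missed by one early stopper**, taking 0.48 as the change at the completer scan (76.3 h).
- Stopped after infusion 1, linear: 0.48 × (1 − 28.3/76.3) = 0.30. Square-root: 0.48 × (1 − √(28.3/76.3)) = 0.19.
- Stopped after infusion 2, linear: 0.48 × (1 − 52.3/76.3) = 0.15. Square-root: 0.48 × (1 − √(52.3/76.3)) = 0.08.

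**Step 3: spurious difference between arm means** = excess share × growth missed.

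| Excess of early stoppers | All after infusion 1 | As % of 0.48 | All after infusion 2 | As % of 0.48 |
|---|---|---|---|---|
| 5% | 0.009-0.015 | 2-3% | 0.004-0.008 | 1-2% |
| 10% | 0.019-0.030 | 4-6% | 0.008-0.015 | 2-3% |
| 20% | 0.038-0.060 | 8-13% | 0.017-0.030 | 3-6% |

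Section 2.2.2 also says that in natural-history studies relative PHE nearly doubles by 72 h. If that is read as a change of 1.0 (an assumption), the percentages stay the same and the infusion-1 range becomes 0.020-0.126.

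**Step 4: is ARDS a likely driver?** It is a stopping criterion (section 7.4), and 6 of the 7 HI-DEF cases were on DFO (section 2.2.3). Section 3.3 puts median onset in those 6 cases at about 76 h from treatment. At the maximum rate, the third infusion here ends at 48 + 4.27 = about 52 h. About half or more of cases with that timing would arise after the last infusion and would not move the scan.

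**The case against.** **A deliberate end-of-exposure measure.** Section 3.3 also says PHE will be examined straight after the infusion is completed, and the footnote knowingly applies the rule to early stoppers. This shows that the anchor is not an oversight. But section 3.3 contrasts that timing only with scanning weeks later. It does not argue for scanning subjects on different days, and the same paragraph names days 3-4.

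**Drug-favoring bias through ARDS.** A reader might infer that the rule will favor DFO, and might put the HI-DEF proportion on DFO (6/21, 28.6%) into the formula with a two-day shift. The documents do not support that. HI-DEF used 62 mg/kg/day for 5 days, this protocol adds exclusions for ARDS risk, and the onset times make ARDS a weak driver. A two-day shift needs a stop before the second infusion. Other routes exist: section 5.2 ends the infusion for recurrent or progressing site irritation. Neither their frequency nor their split by arm is given.

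**Fragile and small.** This stands. The 0.48 is a median from at most 20 DFO-treated subjects over five dose tiers. As a rough scale, assume n = 20 and a normal approximation for a median: SE = 0.33/1.96 = 0.168, and SD = 0.168 × √20/1.253 = about 0.6. With 147 per arm, the SE of a difference is 0.6 × √(2/147) = about 0.07. A spurious difference of 0.009-0.060 is then about 0.1-0.9 SE.

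**The analysis plan can adjust.** It may, and lack of adjustment in the protocol is not a finding. Adjustment cannot fully replace a days 3-4 scan that was never taken.

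**Conclusion.** The point holds as a modest design weakness with a cheap remedy. The scan rule departs from the plan's own days 3-4 target by about 24 h for subjects stopped after infusion 2 and about 48 h after infusion 1. Those subjects stay in the analysis sample with less growth recorded. A difference between arms arises only if stopping differs by arm in frequency or timing. The size, 0.01-0.06 for stops after infusion 1 and about half that or less after infusion 2, rests on an assumed 5-20% excess, two assumed growth shapes and one small Phase I median. The direction by arm is not established.

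PHE is exploratory, so a reader should not carry this over to the futility decision: the day-90 mRS does not depend on the CT. The mismatch between day 5 in the footnote and the 3-day course is a separate, plain inconsistency.

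**What to change.** - Obtain the repeat CT in one fixed window counted from the start of the first infusion, matching days 3-4 and the completer scan time (about 70-82 h if infusions run at the maximum rate; the sponsor should set it from the planned infusion length). Apply it to all subjects still in follow-up, whether or not infusions were stopped.
- Record the actual date and time of the scan.
- Reconcile the surrogate-measures paragraph of section 3.3 with sections 6.1.1 and 6.1.2 and with Table 6.2 and its footnotes, including the day-5 wording against the 3-day course.

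This changes wording only and leaves the number of scans the same. The cost is some missing scans, because some early stoppers will have died, been discharged or withdrawn consent before the window. Time from ICH onset will still vary by up to 24 h, but onset-to-treatment time is already a balancing factor in the randomization.
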